6.4.2 Missing Date Information for Prior or Concomitant Medications

For prior or concomitant medications, including rescue medications, incomplete (ie, partial missing) start date and/or stop date will be imputed. When the start date and the stop date are both incomplete for a subject, impute the start date first.

6.4.2.1 Incomplete Start Date

The following rules will be applied to impute the missing numerical fields. If the stop date is complete and the imputed start date is after the stop date, then the start date will be imputed using the stop date.

Missing day and month

- If the year of the incomplete start date is the same as the year of the date of the first dose of double-blind study drug, then the day and month of the date of the first dose of double-blind study drug will be assigned to the missing fields.
- If the year of the incomplete start date is prior to the year of the date of the first dose of double-blind study drug, then December 31 will be assigned to the missing fields.
- If the year of the incomplete start date is after the year of the date of the first dose of double-blind study drug, then January 1 will be assigned to the missing fields.

Missing month only

- The day will be treated as missing and both month and day will be replaced according to the above procedure.

Missing day only

- If the month and year of the incomplete start date are the same as the month and year of the date of the first dose of double-blind study drug, then the day of the date of the first dose of double-blind study drug will be assigned to the missing day.
- If either the year is before the year of the date of the first dose of double-blind study drug or if both years are the same but the month is before the month of the date of the first dose of double-blind study drug, then the last day of the month will be assigned to the missing day.
- If either the year is after the year of the date of the first dose of double-blind study drug or if both years are the same but the month is after the month of the date of the first dose of double-blind study drug, then the first day of the month will be assigned to the missing day.

6.4.2.2 Incomplete Stop Date

The following rules will be applied to impute the missing numerical fields. If the date of the last dose of double-blind study drug is missing, replace it with the last visit date or data cut-off date if the subject is on-going. If the imputed stop date is before the start date (imputed or non-imputed start date), then the imputed stop date will be equal to the start date.

Missing day and month

- If the year of the incomplete stop date is the same as the year of the date of the last dose of double-blind study drug, then the day and month of the date of the last dose of double-blind study drug will be assigned to the missing fields.
- If the year of the incomplete stop date is prior to the year of the date of the last dose of double-blind study drug, then December 31 will be assigned to the missing fields.
- If the year of the incomplete stop date is after the year of the date of the last dose of double-blind study drug, then January 1 will be assigned to the missing fields.

Missing month only

- The day will be treated as missing and both month and day will be replaced according to the above procedure.

Missing day only

- If the month and year of the incomplete stop date are the same as the month and year of the date of the last dose of double-blind study drug, then the day of the date of the last dose of double-blind study drug will be assigned to the missing day.
- If either the year is before the year of the date of the last dose of double-blind study drug or if both years are the same but the month is before the month of the date of the last dose of double-blind study drug, then the last day of the month will be assigned to the missing day.
- If either the year is after the year of the date of the last dose of double-blind study drug or if both years are the same but the month is after the month of the date of the last dose of double-blind study drug, then the first day of the month will be assigned to the missing day.

7 ANALYSIS CHANGES FROM PROTOCOL

The paired t-test is removed from the analysis on change from baseline in 6-minute walk test, timed function tests, North Star Ambulatory Assessment, Egen Klassifikation Scale, and spirometry endpoints. Subgroup analyses based on 6-minute walk test, corticosteroid type, and the cumulative duration of corticosteroid use are added.

8 CINRG DATA

8.1 Overview of CINRG Data

CINRG is a natural history registry database which collects DMD data using consortium of medical and scientific investigators from academic and research centers on neuromuscular disease. Demographics and baseline characteristics, corticosteroids medication use (and type), efficacy endpoints including 6MWT, time taken to stand from supine, time taken to run/walk 10 meters, NSAA, spirometry, and EK will be analyzed. Other endpoints collected by CINRG but not in Study 019 will not be included into this analysis plan. The CINRG natural history control will be compared to ataluren's efficacy data to assess the ataluren's long- term treatment benefit.

8.2 Matched Populations

To compare CINRG with Study 019, the matched populations are defined in the following table for different endpoints and analyses. Matching criteria will be adjusted if imbalance demographics and baseline characteristics are observed.

Endpoint/ Analysis	Age (Years) at Study Entry	Age (Years) at Assessment	Steroid Use	Ambulation status	Exclude EXON 51 and 45	Baseline value	Visit Year
Age at loss of ambulation	9-18	Not applicable	Cumulative Steroid use duration at study entry ≥ 12 months	Ambulatory at study entry	Yes	time taken to run/walk 10 meters 3.5-26.4 seconds ²	Not applicable
Age at FVC <1 liter	9-18	Not applicable	Not applicable	Non- ambulatory at study entry	Yes	1-3.08	Not applicable
Piece-wise regression based on FVC	Not applicable	≤ 22	Cumulative Steroid use duration at each assessment ≥ 24 months	Non- ambulatory at each assessment	Yes	Not applicable	≥ 2012
%- predicted FVC	9-21	Not applicable	Not applicable	Non- ambulatory at study entry	Yes	32.6- 110.3	Not applicable
%- predicted FEV1	9-21	Not applicable	Not applicable	Non- ambulatory at study entry	Yes	28.1- 104.0	Not applicable
PEF	9-21	Not applicable	Not applicable	Non- ambulatory at study entry	Yes	1.3-218.0	Not applicable
EK	9-18	Not applicable	Not applicable	Ambulatory at study entry	Yes	Score 0-15	Not applicable
6MWT	9-18	Not applicable	Cumulative Steroid use duration at study entry ≥ 12 months s	Ambulatory at study entry	Yes	36-553 meters	Not applicable
time taken to run/walk 10 meters	9-18	Not applicable	Cumulative Steroid use duration at study entry ≥ 12 months	Ambulatory at study entry	Yes	3.5-26.4 seconds	Not applicable
time taken to stand from supine	9-18	Not applicable	Cumulative Steroid use duration at study entry ≥ 12 months	Ambulatory at study entry	Yes	2.3-30 seconds	Not applicable
NSAA	9-18	Not applicable	Cumulative Steroid use duration at study entry ≥ 12 months s	Ambulatory at study entry	Yes	Total score 3-34	Not applicable

8.2.1 Analyses Based on Matched Populations of CINRG and Study 019

Demographics and baseline characteristics (age, race, ambulation status, corticosteroid use (yes or no), duration of corticosteroid use, corticosteroid type, baseline 6MWD, baseline time to run/walk 10 meters, baseline time to stand from supine, baseline %-predicted FEV1, %-predicted FVC, PEF, EK score, NSAA total score) will be summarized descriptively for CINRG and Study 019 based on each matched population. The summary will be displayed by corticosteroid use (yes vs no) and cumulative steroid use (≥ 12 months vs < 12 months) for baseline ambulatory and non-ambulatory subjects separately. In general, the baseline is defined as the first visit in CINRG data. The baseline age in the FVC analysis using piece-wise regression models is the age at the first FVC assessments for both CINRG and Study 019.

The comparison to the natural history data (ie, CINRG data) based on matched subjects will be performed in FVC using piece-wise regression models, age to loss of ambulation, and age to FVC < 1 liter using Kaplan-Meier method.

Piece-wise regression models will be applied to log FVC in CINRG and Study 019 data, separately, using different ages as the changepoint. The most possible changepoint in terms of age will be chosen at the best model fit (ie, AICC value is the maximal). Scatter plots of log FVC and the most fitted piece-wise regression line will be generated for CINRG and Study 019, separately. Comparison between the observed and predicted FVC in Study 019 will be performed using repeated measures analysis of variance to account for within-subject correlation, where the predicted values are based on the regression equation estimated by the best fit regression model based on CINRG data.

The Kaplan-Meier method will be applied to the analysis of age to loss of ambulation and age to FVC < 1 liter. The median age to loss of ambulation and median age to FVC < 1 liter will be reported. The comparison between Study 019 and CINRG will be conducted via log-rank test by corticosteroid use at baseline (yes or no) and overall. The Kaplan-Meier curves will also be displayed.

In Study 019, the loss of ambulation is defined as the disease progression reported as the adverse event or the time to run/walk 10 meters > 30 seconds, whichever occurs earlier. The event age is the one on the AE start date. The subjects who are ambulatory at the end of study will be censored on the last valid timed function tests assessment date. Age on that date will be used in the analysis. In the CINRG data, the age at the earliest report of the non-ambulation or the time to run/walk 10 meters > 30 seconds, whichever earlier, will be picked as the event age. If subjects in CINRG data do not report non-ambulation, the age at the last report of ambulation will be chosen as the censor age. A sensitivity analysis will be performing based on the loss of ambulation defined only by disease progression AE.

Similarly, the age at FVC < 1 liter is the one at the first time FVC < 1 liter. If subjects do not have FVC < 1 liter, the age at the last non-missing FVC assessment will be chosen as the censor age.

For CINRG data only, the observed values will be summarized descriptively for each actual age on 6MWT, time to run/walk 10 meters, time to stand from supine, NSAA total and linear scores, %-predicted FVC, %-predicted FEV1, PEF and EK total scores by corticosteroid use at baseline (yes or no) and overall based on the matched populations.

NSAA score derivation algorithms in Study 019 will be applied to CINRG data.

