DBMD usually first manifests in boys ~3 to 7 years of age when they are noted to develop lordosis, a waddling gait, and the Gowers' sign (a characteristically abnormal method of rising from a supine to a standing position) [Brooke 1989, McDonald 1995, Boland 1996, Worton 2001]. Inexorable progressive weakness is seen, particularly in the proximal musculature. Ambulation becomes increasingly abnormal. By the age of 8 years, most boys have difficulty rising from the floor and ascending stairs and they often fall while walking. Boys with the disease spend less time walking and walk more slowly than healthy boys [McDonald 2005a] and are significantly less active than normal boys of similar age [McDonald 2002, McDonald 2005b]. By 10 to 14 years of age, most are wheelchair-bound. In ambulatory DMD boys, the most frequent cardiac abnormality is sinus tachycardia and heart rate variability, occurring from childhood and persisting throughout life [Finsterer 2003, Gulati 2005]. Pulmonary function is usually normal before 10 years of age and is well maintained into adolescence in boys receiving corticosteroids [Mendell 1989, Griggs 1991, Phillips 2001, Tangsrud 2001, Biggar 2001, Biggar 2006]. Later in adolescence, cardiac and diaphragmatic muscles become progressively weaker and patients require treatment for cardiac insufficiency and ventilatory support. Patients usually die of cardiac or pulmonary failure by 15 to 22 years of age [Brooke 1989, McDonald 1995, Simonds 1998, Worton 2001, Eagle 2002].

2.2. **Ataluren (PTC124)**

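### The overall Study 019 versus CINRG log-rank for age at FVC below 1 litre is neither matched on nor stratified by corticosteroid use, so a steroid imbalance could bias it in either direction

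*SAP*

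**What the plan says.** The table in SAP 8.2 defines a separate matched population for each endpoint. Its columns are age at entry, age at assessment, steroid use, ambulation status, exon exclusion, baseline value and visit year. The row in question is "Age at FVC <1 liter". Read across, it begins "Age at FVC <1 liter 9-18 Not applicable Not applicable Non- ambulatory at study entry", and the second of the two inapplicable cells is the steroid column. The piece-wise regression row, which analyses the same measure, requires "Cumulative Steroid use duration at each assessment ≥ 24 months". Age at loss of ambulation, 6MWT, the two timed tests and NSAA each require at least 12 months of cumulative use at study entry.

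SAP 8.2.1 gives the test: "The comparison between Study 019 and CINRG will be conducted via log-rank test by corticosteroid use at baseline (yes or no) and overall". It describes no stratified or covariate-adjusted version of the overall test.

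Two protocol statements bear on this. Section 2.1 says that pulmonary function "is well maintained into adolescence in boys receiving corticosteroids". Section 1.1 notes that steroid treatment is not universal, particularly once ambulation is lost. SAP 8.1 says the CINRG comparison is meant to assess the long-term benefit of ataluren.

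**The concern.** CINRG is an external control, so nothing in the design balances steroid use between the cohorts. On the protocol's own account steroids preserve lung function, and their use varies among non-ambulatory patients, who make up this matched set. A prognostic factor that may differ between the cohorts is therefore left out of both the matching and the overall test. Any difference in steroid use would enter the age-at-FVC comparison as if it belonged to ataluren.

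The sponsor already treats steroids as relevant to this endpoint. SAP 5.9.2 and 5.9.3 plan Study 019 subgroup analyses of age at FVC below 1 litre by steroid type and by cumulative duration (under 12 months against 12 months or more). The SAP gives no reason for handling FVC one way in the piece-wise analysis and another way here.

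**Working it through.** The plan gives no event count, alpha, power, steroid prevalence or CINRG sample size for this comparison, so there is no figure to reproduce. What follows shows how large the bias could be. Every numerical input is an assumption.

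**Step 1: closed-form bias with no drug effect.** Let h be the hazard ratio for FVC below 1 litre, steroid users against non-users. Let p1 and p0 be the proportions using steroids in Study 019 and CINRG. At the start of follow-up the apparent hazard ratio, Study 019 against CINRG, is

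(p1·h + 1 − p1) / (p0·h + 1 − p0)

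| Steroid use, 019 vs CINRG | h = 0.7 | h = 0.5 |
|---|---|---|
| 80% vs 60% | 0.76/0.82 = 0.93 | 0.60/0.70 = 0.86 |
| 90% vs 70% | 0.73/0.79 = 0.92 | 0.55/0.65 = 0.85 |
| 80% vs 50% | 0.76/0.85 = 0.89 | 0.60/0.75 = 0.80 |
| 90% vs 60% | 0.73/0.82 = 0.89 | 0.55/0.70 = 0.79 |
| 70% vs 90% (reversed) | 0.79/0.73 = 1.08 | 0.65/0.55 = 1.18 |

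**Step 2: effect on the test.** A simulation with no ataluren effect used 4,000 trials per scenario. It assumed exponential times from entry with a median of 5 years off steroids, censoring at 5 years, 30 vs 60 or 45 vs 100 patients (Study 019 vs CINRG), h of 0.7, 0.5 or 0.35, and a nominal two-sided 5% level. Ranges run over h and sample size.

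| Steroid use, 019 vs CINRG | Apparent HR | Unstratified rejection | Stratified rejection |
|---|---|---|---|
| 80% vs 80% | about 1.00 | 4.6–5.4% | 4.8–5.7% |
| 90% vs 70% | 0.92 to 0.78 | 5.1–9.9% | 4.6–5.5% |
| 90% vs 50% | 0.87 to 0.65 | 6.5–27% | 4.8–5.8% |
| 70% vs 90% | 1.07 to 1.31 | 5.8–12.3% | 4.7–5.6% |

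The Monte Carlo standard error at 5% is √(0.05 × 0.95 / 4000), or 0.34 percentage points, so the stratified test stays close to nominal throughout.

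**Step 3: limits of the illustration.** The closed form describes the start of follow-up and fades somewhat as higher-risk patients have events. At h = 0.35 and 90% vs 70% it gives 0.415/0.545 = 0.76, against 0.78 simulated. The simulation runs on time from entry, while the SAP analyses age. It also assumes that baseline yes/no carries the whole steroid effect, so the stratified results are a best case.

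**The case against.** A reader might infer that the SAP ignores steroids in its pulmonary comparisons. It does not. SAP 8.2.1 plans log-rank tests within baseline users and non-users, and those tests control the same variable that a stratified test would use. If the overall and within-group results disagreed, the output would show it. This stands, but it does not repair the overall test. Enrolment was capped at about 96, and this row keeps only patients who are non-ambulatory at entry, aged 9 to 18, with baseline FVC of 1 to 3.08. Splitting that set gives two small tests, and nothing pools them.

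A reader might also extend the point to %-predicted FVC, %-predicted FEV1 and PEF, whose rows likewise carry no steroid criterion (for example "predicted FVC 9-21 Not applicable Not applicable Non- ambulatory at study entry"). The log-rank argument does not reach them. SAP 8.2.1 limits the CINRG comparisons to piece-wise FVC, age at loss of ambulation and age at FVC below 1 litre. For those three measures CINRG is only summarised descriptively by age, by steroid use and overall. The EK row has the same empty steroid cell and the same descriptive treatment.

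Nor do the documents support calling the overall test the main pulmonary result. No section ranks the comparisons, the primary endpoint is safety (SAP 3.3), and SAP 1 presents CINRG as help in understanding long-term data.

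Safeguards exist. Steroid use, duration and type are tabulated for both cohorts, and SAP 8.2 allows the matching criteria to be changed if imbalance appears. That clause names no variable, threshold or procedure and would operate after the data are seen, so it is a weak answer. There is also a plausible reason, though not one the SAP gives, for setting no duration rule in non-ambulatory rows: steroids are used less consistently there. That is a reason not to restrict the sample, but it does not argue against stratifying.

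**Conclusion.** The point holds for age at FVC below 1 litre. Steroid use is not matched, and the only full-set test has no stated adjustment for it. Under assumed steroid hazard ratios of 0.5 to 0.7 and 20 to 30 points more steroid use in Study 019, the spurious hazard ratio is about 0.79 to 0.93. With 70% against 90% it is 1.08 to 1.18, which works against ataluren. At the more modest simulated gap (90% vs 70%) the false-positive rate is 5.1 to 9.9%, a limited inflation. It reaches 27% only with a 40-point gap, a steroid hazard ratio of 0.35 and the larger sample size.

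It would be too strong to say that the comparison will show a false ataluren benefit. The documents report no imbalance, so neither the direction nor the size of the bias is known. The case for changing the plan is that the correction is nearly free and works in both directions.

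**What to change.** In SAP 8.2.1, state that the overall Study 019 versus CINRG comparison of age at FVC below 1 litre is a log-rank test stratified by baseline corticosteroid use (yes or no), or a Cox model with steroid use as a covariate, on the full matched set. Keep the within-group tests beside it. Stratification leaves the overall Kaplan-Meier curves and medians unadjusted, so show these by steroid group as well.

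Add a sensitivity analysis by cumulative use at entry (12 months or more against less than 12). Using it as a stratification factor keeps everyone, whereas restricting to 12 months or more, as the ambulation rows do, would shrink the sample. State as a limitation that yes/no stratification leaves duration and steroid type uncontrolled.

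The cost is a line of SAP wording for the main change and a short addition for the sensitivity analysis. Steroid use and duration are already summarised for both cohorts, so no new data are needed and the main analysis loses no subjects.

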3.3. Clinical Endpoints

Primary

• Safety profile characterized by type, frequency, severity, timing, and relationship to ataluren of any adverse events or laboratory abnormalities

Secondary

• In ambulatory patients, change from baseline in 6MWD as measured by the 6-minute walk test (6MWT)

- In ambulatory patients, change from baseline in physical function as measured by the North Star Ambulatory Assessment (NSAA)
- In ambulatory patients, change from baseline in timed function tests (time to stand from supine and time to run/walk 10 meters)
- In nonambulatory patients, change from baseline in pulmonary function as measured by spirometry
- In nonambulatory patients, change from baseline in patient and parent/caregiver-reported activities of daily living, as measured by the Egen Klassifikation (EK) scale
- In all patients, changes in patient and/or parent/caregiver reports of disease status as measured by a standardized survey administered by site personnel

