7.2.19. Egen Klassifikation Scale

Activities of daily living will be measured using the EK scale [Steffensen 2001] in nonambulatory patients (unable to run/walk 10 meters in ≤30 seconds). The EK scale will be completed at Screening (Visit 1), Week 48 (Visit 6), Week 96 (Visit 10), and Week 144 (Visit 14), Week 192 (Visit 18), and Week 240 (Visit 22 End-of-Treatment/Premature Discontinuation).

Please refer to the Study Manual for further details on how to administer the EK scale.

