13.2.6.4 Egen Klassifikation

For nonambulatory patients with DMD, the EK scale has been selected to assess functional ability after loss of ambulation [Steffensen 2001]. The EK scale has previously been shown to be highly reliable when tested for intra- and inter-rater reliability among patients with DMD [Steffensen 2002a, Steffensen 2002b].

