3.3 Study Endpoints

Primary:

- Safety profile characterized by type, frequency, severity, timing, and relationship to ataluren of any adverse events or laboratory abnormalities

Secondary:

- In ambulatory subjects,
 - i. change from baseline in 6MWD as measured by the 6-minute walk test (6MWT)
 - ii. change from baseline in physical function as measured by the North Star Ambulatory Assessment (NSAA)
 - iii. change from baseline in timed function tests (time to stand from supine and time to run/walk 10 meters)
- In non-ambulatory subjects,
 - i. change from baseline in pulmonary function test - % predicated forced vital capacity (FVC) and % predicted forced expiratory volume in 1 second (FEV1) as measured by spirometry
 - ii. change from baseline in patient and parent/caregiver-reported activities of daily living, as measured by the Egen Klassifikation (EK) scale

- All subjects,
 - i. changes in patient and/or parent/caregiver reports of disease status as measured by a standardized survey administered by site personnel

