5.8.4 Egen Klassifikation Scale

The total score of EK scale and change from baseline to each post baseline visit will be summarized descriptively by visit for non- ambulatory subjects and As-Treated population. Similarly the total score will also be summarized for each actual age.

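### The EK row of the SAP's matched-population table selects boys ambulatory at entry, although EK is a nonambulatory endpoint, so the CINRG EK summary is not a like-for-like reference for the nonambulatory EK results

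*SAP*

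**What the plan says.** The protocol treats EK as a nonambulatory measure in three places.

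- Section 3.3 lists the endpoint as "In nonambulatory patients, change from baseline in patient and parent/caregiver-reported activities of daily living, as measured by the Egen Klassifikation (EK) scale".
- Section 7.2.19 has the scale completed from Screening onward "in nonambulatory patients (unable to run/walk 10 meters in ≤30 seconds").
- Section 13.2.6.4 gives the reason: "For nonambulatory patients with DMD, the EK scale has been selected to assess functional ability after loss of ambulation".

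SAP 3.3 keeps the same endpoint under its non-ambulatory heading. SAP 5.8.4 says that the EK total score and its change from baseline "will be summarized descriptively by visit for non- ambulatory subjects and As-Treated population", with a similar summary by actual age.

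The matched-population table in SAP 8.2 sets the EK criteria as entry age 9-18, no steroid criterion, and "Ambulatory at study entry Yes Score 0-15". SAP 8.2.1 uses the matched sets for EK in two ways. Baseline characteristics are described for both cohorts on each matched population. In addition, "For CINRG data only, the observed values will be summarized descriptively for each actual age", and EK total score is among the measures listed there.

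**The concern.** The row places EK in the opposite ambulation stratum from its endpoint definition. It also asks for a baseline score that the protocol does not schedule for that stratum.

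SAP 8.1 names EK among the endpoints to be analysed and gives the purpose of the CINRG control as assessing ataluren's long-term benefit. A reader will therefore set the CINRG by-age EK table beside the Study 019 by-age EK table. If the first holds boys who were walking at entry and the second boys who were not, disease stage at entry differs between the tables. Any difference at a given age could then reflect stage rather than treatment.

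**Working it through.** No sample size, power or error rate is involved. The check is a comparison of definitions and a hand count of the SAP 8.2 table.

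**Can a Study 019 boy meet the EK row?**
1. SAP 4 classifies ambulation at entry by the Screening 10-meter time: 30 seconds or less is ambulatory, more than 30 seconds is not.
2. SAP 6.2 defines baseline as the last valid value on or before the first dose.
3. Protocol 7.2.19 gives EK to boys who cannot cover 10 meters within 30 seconds.
4. A boy who is ambulatory at Screening should therefore have no EK score then, and so no baseline EK. If 7.2.19 was followed, no Study 019 boy satisfies both conditions of the row.

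**Whom does the row exclude?** Any boy nonambulatory at entry, in either cohort. SAP 8.2.1 displays the matched baseline tables separately for ambulatory and non-ambulatory boys. For the EK set, the non-ambulatory panel is empty by the row's own rule.

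**How does the row compare with the other ten?**

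| Feature | Ambulatory rows (6: age at loss of ambulation, EK, 6MWT, run/walk 10 m, stand from supine, NSAA) | Nonambulatory rows (5: age at FVC <1 liter, piece-wise FVC, %-predicted FVC, %-predicted FEV1, PEF) |
|---|---|---|
| Steroid criterion | At least 12 months in 5; not applicable in 1 (EK) | Not applicable in 4; at least 24 months in 1 (piece-wise FVC) |
| Entry age | 9-18 in all 6 | 9-18 in 1 (age at FVC <1 liter); 9-21 in 3; not applicable in 1 |

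EK is the only ambulatory row without a steroid criterion. Its age and steroid entries equal those of the nonambulatory row for age at FVC <1 liter. That pattern is consistent with a dropped prefix but does not prove one, since the 9-18 range also fits the ambulatory rows.

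**Does another section explain the row?** SAP 7 lists the changes from the protocol and mentions none to the EK population. The SAP 8.2 clause on adjusting the matching criteria is triggered by observed imbalance in demographics and baseline characteristics, not by a criterion that contradicts the endpoint. SAP 1 lets the SAP override the protocol in a conflict, so the row would be programmed as it stands.

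**What output is affected?** SAP 8.2.1 names the comparisons with CINRG as piece-wise regression of FVC, age at loss of ambulation and age at FVC <1 liter. EK is not among them. Its exposure is the baseline table for the EK matched set and the CINRG by-age summary.

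**The case against.** Four fair points can be made on the other side.

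- **SAP 5.8.4 is not confined to nonambulatory boys.** It also covers the As-Treated population, and SAP 5.1 calls for analyses by baseline ambulatory status unless specified otherwise. EK output for Study 019 boys ambulatory at entry is therefore provided for, if data exist. This stands: the mismatch is with the nonambulatory summary, not with every planned EK table.
- **Protocol 7.2.19 is not limited to status at entry.** The sections on 6MWT, timed tests, NSAA and the Brooke scale do say at study entry. A boy who stops walking during the roughly 240 weeks can have later EK scores. This also stands, but it does not supply the baseline score that the row requires.
- **Ambulatory boys may have been scored at Screening.** Both schedules mark EK there without restriction, and a range as specific as 0-15 looks taken from data. This is possible but unproven. The protocol's schedule is equally unrestricted for 6MWT and spirometry, which 7.2.16 and 7.2.20 then restrict, and Protocol 7.1 refers the reader to 7.2. If such boys were scored, the SAP should say so.
- **The output is only descriptive.** This is correct, and it limits the weight of the point.

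A reader might go further and infer that the matched set has 0% overlap with the EK population, omits every boy for whom the endpoint is defined, and biases the comparison against ataluren. The documents do not support this in general. It follows only if the CINRG table is read against the nonambulatory-at-entry table. Against the As-Treated summary, the overlap depends on counts that are not given. Against Study 019 boys ambulatory at entry, this stage difference does not arise.

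**Conclusion.** The EK row contradicts the endpoint definition in both documents, and nothing in either resolves it. As written, the CINRG by-age EK summary and the baseline table for the EK matched set exclude boys nonambulatory at entry. They cannot act as a like-for-like reference for the SAP 5.8.4 nonambulatory summary.

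The consequence is confined to descriptive tables. That the Study 019 side of the set would be empty rests on the assumption that sites followed 7.2.19. The documents do not show whether CINRG scored ambulatory boys or which group the 0-15 range came from. They give no stratum counts, so neither the size nor the direction of a bias can be stated. The point merits correction because the row is wrong as written and cheap to put right, not because it threatens a formal result.

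**What to change.** In the SAP 8.2 EK row, change the ambulation criterion to nonambulatory at study entry for both cohorts. Re-derive the baseline-score range and the entry-age range from that group. Produce the Study 019 by-age EK table on the same matched set, so that both sides follow one rule.

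If an ambulatory-at-entry set is intended, justify it in the SAP, state where its baseline EK comes from given Protocol 7.2.19, and read it only against Study 019 boys ambulatory at entry.

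The cost is one table row and a rerun of the EK baseline and by-age tables. No new data are needed.
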